5.0 SELECTION AND WITHDRAWAL OF SUBJECTS

5.1 Patients with biopsy-proven DCIS, mammographic and CE-MRI evidence of DCIS measuring ≤ 4 cm, and a desire to receive breast conserving therapy, will be considered for participation in this study.

5.2 Patient history, physical examination findings, and demographics (sex, age, height, weight, bra size, etc.) will be performed and documented.

5.3 Inclusion Criteria for Initial Registration (all patients cohorts):

5.3.1 All cohorts

- a. Signed informed consent and HIPAA documents
- b. Female sex
- c. Age ≥ 40 years

- d. Localized ductal carcinoma in situ
- e. Clinically and/or histologically negative axillary lymph nodes
- f. No imaging or clinical findings suggestive of invasive carcinoma.

5.3.2 Cohort 1 (Immediate IORT group)

- a. Localized DCIS measuring ≤ 4 cm on preoperative imaging.

5.3.3 Cohort 2 (Delayed IORT group)

- a. Localized DCIS measuring ≤ 4 cm or less on surgical pathology

- i. Delayed IORT could be performed for the explicit purpose of administering IORT or performed following re-excision of a previously operated breast to achieve clear surgical margins.
- ii. This cohort includes patients who were excluded from immediate IORT based on pre-operative imaging suggesting ineligibility for immediate IORT, but who are subsequently found to meet histological criteria (localized DCIS ≤ 4 cm and no invasive cancer) for IORT based on surgical pathology.
- iii. Unifocal microinvasive (T1mic or invasive focus ≤ 1 mm in maximal diameter) is allowed following initial WLE if surgical pathology margins were ≥ 2 mm for both the invasive and non-invasive components.
- iv. Delayed IORT must be performed within 3 months of initial WLE.

5.3.4 Cohort 3

- a. Subjects who received IORT at the time of initial WLE but whose surgical pathology indicates the need for further therapy:
 - i. DCIS measuring greater than 5 cm on surgical pathology.
 - b. Surgical margins width < 2 mm.

5.4 Exclusion Criteria for Initial Registration (all patient cohorts)

- 5.4.1 Male sex
- 5.4.2 Age < 40
- 5.4.3 DCIS associated with any evidence of microinvasion or invasive carcinoma on pre-operative imaging or core biopsy of the breast or axillary nodes.
- 5.4.4 DCIS that is multicentric in the ipsilateral breast. Multicentricity will be defined at 2 or more lesions separated by more than 3 cm in the same breast.
- 5.4.5 Non-epithelial breast malignancies such as sarcoma or lymphoma
- 5.4.6 DCIS associated with diffuse suspicious or indeterminate microcalcifications
- 5.4.7 Pregnancy or lactation
- 5.4.8 Collagen vascular diseases, including Systemic lupus erythematosus, Systemic sclerosis (scleroderma), CREST Syndrome (calcinoses, Raynaud phenomenon, esophageal dysfunction, sclerodactyly, telangiectasia, and the presence of anticentromere antibodies), polymyositis, dermatomyositis with a CPK level

above normal or with an active skin rash, inclusion-body myositis, or amyloidosis

5.4.9 Serious psychiatric or addictive disorders

5.5 Withdrawal from Study

During the course of the study, it is possible that patients and/or device systems may be withdrawn from the study. Factors that may lead to a withdrawal from the study may include, but are not limited to the following:

- 5.5.1 Patient Withdrawal – At any time a patient may voluntarily withdraw from the study. This withdrawal will not affect her future medical treatment.
- 5.5.2 Patient Lost to Follow-Up – Should a patient be classified as lost to follow-up, efforts to contact the patient will be made.
- 5.5.3 Physician Decision – Should a physician decide that the constraints of the protocol are detrimental to the health and welfare of the patient, the patient may be withdrawn from the study.
- 5.5.4 Medical Reason – Should the patient's condition deteriorate, the patient may be withdrawn from the study to allow for proper medical care.

6.0 STRATIFICATION/DESCRIPTIVE FACTORS/RANDOMIZATION SCHEME

Patient Selection. This is not a randomized study. The trial will be open to 3 cohorts of patients with a diagnosis of DCIS breast, as outlined in the inclusion criteria (Section 3.0).

7.0 STUDY AGENT ADMINISTRATIONS OR INTERVENTION AND TOXICITY MANAGEMENT PLAN

7.1 Patient Surgery and IORT

- 7.1.1 Each patient will undergo WLE to remove DCIS and to create a cavity. Each of the following procedures qualifies as WLE: breast conserving surgery, lumpectomy, segmental mastectomy, segmental resection, and partial mastectomy.
- 7.1.2 Recognizing the potential for DCIS to be larger than demonstrated on imaging, the surgeon will aim to excise the lesion with surgical margins of 10 mm. Multiple localizing wires will be placed pre-operatively to facilitate resection.
- 7.1.3 Due to the potential for finding occult microinvasive carcinoma in the final surgical pathology, sentinel node biopsy will be allowed at the discretion of

the surgeon.

- 7.1.4 At the conclusion of IORT, surgical clips will be placed in the resection cavity to mark the surgical margins to facilitate re-excision, if indicated.
- 7.2 Criteria for Receiving Additional therapy after IORT (Cohort 3)
 - 7.2.1 Patients with DCIS >5 cm will be advised to undergo WB-EBRT (or mastectomy) despite having received IORT, even if surgical margins are clear (\geq 2mm).
 - 7.2.2 Patients with surgical margins width of <2 mm following local excision and immediate IORT will be advised to undergo re-excision. If residual disease is found and new final margins are <2 mm, the patient will be advised to undergo WB-EBRT. However, no addition therapy will be needed if no residual disease is found, or if final margins is \geq 2mm.

7.3 Ancillary treatments.

Neoadjuvant hormonal therapy (e.g., Tamoxifen or Fulvestrant) and chemopreventive therapy (e.g., green tea extract) will be allowed provided that the total duration of neoadjuvant hormonal or chemopreventive therapy does not exceed 30 days prior to WLE and immediate IORT.

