- c. Protection of Adjacent Tissues. Delivery of radiotherapy at the time of surgery allows the surgeon to protect adjacent tissues from exposure to excessive radiation, e.g., by placement of internal radiation barriers on the surface of the pectorals major muscle to protect the underlying heart and lung, and by retraction of the skin away from the radiation source to reduce skin toxicity.
- d. Lower Cost. Since IORT allows the entire radiation therapy to be given in one dose rather than multiple doses, the cost of IORT is lower than other forms of radiotherapy. For example, at the USC Kenneth Norris

Comprehensive Cancer Hospital, the cost of IORT using the Intrabeam PRS is approximately \$7500 per patient compared to \$9000 for WB-EBRT and \$28,000 for MammoSite balloon catheter brachytherapy¹⁶.

1.2.2 While IORT for DCIS offers many advantages over alternative forms of breast radiotherapy, it also has several important limitations:

- a. Incomplete Pathology Results. The IORT dose is delivered before the surgical pathology results (e.g., margin status) are fully known. As a result, IORT might be given prematurely or inappropriately in patients who are later found to have more extensive disease than initially anticipated. Inadequate surgical margins will necessitate re-excision or conversion to mastectomy, either of which will increase the cost and potential morbidity of breast cancer therapy. These risks can be partially reduced with the use of Intraoperative margin assessment (e.g., frozen sections and specimen radiography) to aid identification of close or inadequate margins.
- b. Possible Need for Additional Radiotherapy. Patients found to have inadequate surgical margins after having received IORT may require the addition of WB-EBRT (with or without re-excision). Generally, repeat IORT is not permitted. The addition of WB-EBRT not only increases the cost of radiotherapy, it may also, theoretically, increase the morbidity of radiotherapy. However, based on several studies in invasive breast cancer patients evaluating IORT administered at a boost dose of 1000 rads to the tumor bed, followed by routine WB-EBRT, there is good evidence to suggest that WB-EBRT given after IORT can be administered with good to excellent cosmesis and no grade 3 or 4 adverse effects¹⁷⁻¹⁹. Currently, there are no published data specifically reporting the efficacy and safety of IORT (with or without combined WB-EBRT) for the treatment of DCIS.

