10.0 CRITERIA FOR EVALUATION AND ENDPOINT DEFINITIONS

10.1 Feasibility Endpoint. The primary efficacy endpoint of the treatment will be re-operation (re-excision or mastectomy) rates following WLE and IORT.

Re-excision (or mastectomy) will be indicated for patients with microscopic surgical margins measuring <1 mm following WLE and immediate IORT.

Additionally, the following data will also be reported and analyzed:

10.1.1 Indications for WB-EBRT. Patients with margins that are margins < 2 mm after reexcision for <2 mm margins, or, DCIS > 5 cm.

10.1.2 Extent of disease. Extent of disease will be determined by measuring the dimensions of the DCIS lesion as demonstrated by pre-operative mammography and CE-MRI and the dimensions of the DCIS lesion contained within the surgical resection specimen

10.1.3 Surgical Margins. Surgical margins will be defined as the distance from the closest tumor cells to the cut or inked edge of the surgical specimen.

10.1.4 DCIS histopathology. DCIS histopathology will be determined by evaluating the histopathological type, grade (histological, nuclear, and mitotic), the presence or absence of comedonecrosis or invasive carcinoma in the pre-operative biopsy and the surgical specimen.

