13.1 Study Design and Sample Size Justification

The study design was selected based on the primary aim: to evaluate the ability of CE-MRI and mammography to identify patients for whom IORT is not optimal because of the inability to achieve sufficiently wide surgical margins. If 15% or fewer patients require re-excision, this would be considered acceptable and encouraging for further study; however, a reexcision rate of 30% or higher would not be acceptable.

13.1.1 Accrual to Cohort 1 (Specific Aims 1-3 in Sections 2.1 – 2.3).

Patients will be enrolled in Cohort 1 until 79 patients have received immediate IORT. All patients who are deemed eligible for IORT based on mammography and CE-MRI results will be considered in the decision to stop or continue the trial. There will be one interim analysis when 25 patients have completed WLE and immediate IORT, whether or not additional therapy is needed.

After 25 patients have been evaluated, if 19 or more did NOT require re-excision (based on the surgical specimen), then accrual will continue until 79 patients undergo WLE and immediate IORT. If 7 or more of the initial 25 needed re-excision, then the study will terminate and investigators will conclude that the current method for staging is not sufficiently accurate.

After 79 patients have been evaluated, if 62 or more did NOT need re-excision (based on surgical specimen), investigators will conclude that the chance of correctly identifying a tumor that is suitable for IORT is greater than 70% and that further study of the approach would be justified. If 18 or more of the initial 79 needed re-excision, then investigators will conclude that the chances of correctly identifying a tumor that is suitable for IORT is less than 85%. In this instance, investigators would aim to improve the staging procedures before continuing with this approach.

With this Simon optimal 2-stage design, there will be a 5% chance (alpha) of incorrectly deciding that that approach warrants further study, when the true chance of correctly staging is less than 85%; and there will be a 10% chance (beta) of correctly deciding that this approach warrants further study, when the true chance of correctly staging is greater than 70%.

To evaluate the safety and tolerability of immediate IORT, the following side effects or complications will be taken as evidence that IORT was not well tolerated:

- a. any Grade 2 or greater toxicity

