13.1.3 Accrual to Cohort 3 (Specific Aim 5 in Section 2.5)

Cohort 3 will be a subset of patients who begin in Cohort 1 (i.e. are deemed candidates for immediate IORT and who receive immediate IORT) but who subsequently are found to require a mastectomy, re-excision alone, re-excision followed by WB-EBRT, or WB-EBRT alone. This cohort will be followed to monitor and document the complications of the mastectomy and WB-EBRT (with or without re-excision) which are performed following IORT. If all 79 patients are enrolled in Cohort 1 (i.e. the study is not stopped early), then we would expect between 8 and 17 patients requiring an additional surgical procedure (mastectomy or re-excision); as soon as 18 patients require an additional surgical procedure, the study will be terminated.

Using the same definition of unacceptable toxicity as above in 13.1.1 for Cohort 1 and in 13.1.2 for Cohort 2 (any Grade 2 or greater toxicity, or failure for the surgical incision to heal as evidenced by wound dehiscence,

wound infection, or skin ulceration), the rules in Table 3 will also be applied to the patients undergoing an additional surgical procedure in Cohort 3. Separately, we will evaluate the tolerability of WB-EBRT following IORT, in the same manner (using Table 3). Unacceptable toxicity of WB-EBRT include any Grade 2 or greater toxicity, skin flap necrosis, skin ulceration, wound dehiscence, or brachial plexopathy.

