13.2 Analysis of Results

The outcome of all patients who are registered onto this study will be reported. The results of patients in Cohorts 1, 2, and 3, will be summarized separately.

For those patients whose CE-MRI and mammography results suggested that they would be candidates for IORT (i.e. Cohort 1), the surgery results will be summarized in terms of whether or not a re-operation was indicated (because of inadequate margins or for any other reason) or whether or not WB-EBRT was recommended (because of small margin size or large tumor size, or another reason). For those patients who subsequently underwent re-excision +/- WB-EBRT or who subsequently received WB-EBRT alone (or mastectomy), all complications and side effects will be summarized.

For all patients, the size of the lesion as estimated by the imaging modalities will be compared to the size measured in the surgical specimen.

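### For DCIS >5 cm with clear margins, whether a patient is a primary failure depends on the section read and on whether mastectomy or WB-EBRT follows

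*Combined protocol and SAP*

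**What the plan says.** Section 7.2.1 gives two possible treatments for a large lesion with adequate margins and no rule for choosing between them: "Patients with DCIS >5 cm will be advised to undergo WB-EBRT (or mastectomy) despite having received IORT, even if surgical margins are clear".

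Four places then describe what is counted:

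- **10.1 (endpoint definition):** "The primary efficacy endpoint of the treatment will be re-operation (re-excision or mastectomy) rates following WLE and IORT". Mastectomy is in and WB-EBRT is not. The next sentence of 10.1 ties the indication for re-operation to margin width.
- **13.1.1 (decision rules):** the trial continues after 25 patients "if 19 or more did NOT require re-excision (based on the surgical specimen"), and succeeds after 79 if at least 62 "did NOT need re-excision (based on surgical specimen"). Mastectomy is not named, and the opening of 13.1 ties the aim to achieving sufficiently wide margins.
- **13.1.3 (Cohort 3):** "as soon as 18 patients require an additional surgical procedure, the study will be terminated". The same paragraph explains an additional surgical procedure as mastectomy or re-excision and does not restrict the reason.
- **13.2 (analysis):** Cohort 1 results are summarised by "whether or not a re-operation was indicated (because of inadequate margins or for any other reason").

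Sections 2.2 and 13.0 place the need for WB-EBRT under a separate, secondary aim.

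**The concern.** Take two women with the same imaging and the same pathology: DCIS above 5 cm, margins clear. One has mastectomy and the other WB-EBRT. Imaging underestimated the lesion equally in both. Under 10.1 (first sentence) and 13.1.3 the first is a primary failure and the second is only an Aim 2 case. Under 13.1.1 neither is a primary failure.

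The need-based wording of 13.1.3 and 13.2 does not settle this. For a size-only finding, 7.2.1 advises either a surgical or a non-surgical course, so pathology alone cannot say whether an operation was required or indicated. In practice the treatment taken will decide.

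At stake are the primary endpoint and the only feasibility stopping rule of a single-arm trial of 79 patients. Since 79 − 62 = 17, the trial succeeds with 17 failures and fails with 18, so the scoring of one or two patients can decide it.

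**Working it through.** **1. Inputs from the documents (13.1 and 13.1.1).** Unacceptable failure rate 30%, acceptable 15%; alpha 5%, beta 10%. Stage 1: 25 patients, continue with at least 19 successes (at most 6 failures). Final: 79 patients, favourable with at least 62 successes (at most 17 failures).

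**2. Reproduce the plan's design.** With true failure rate q:

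P(go) = Σ over x = 0…6 of Bin(x; 25, q) × P(Y ≤ 17 − x), where Y ~ Bin(54, q).

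- q = 0.30: P(go) = 0.0492 (plan: alpha 5%).
- q = 0.15: P(go) = 0.9041, so beta = 0.096 (plan: 10%).

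A full search for the Simon optimal design with these inputs returns the same cut-offs (18/25 and 61/79 as the largest unfavourable success counts). The design is sound as computed. The question is only what goes into q.

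**3. How each section scores DCIS >5 cm with clear margins.**

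| Section | Mastectomy follows | WB-EBRT follows |
|---|---|---|
| 10.1, first sentence | counts | does not count |
| 13.1.3, stop at 18 | counts | does not count |
| 13.2, any other reason | counts | does not count as re-operation |
| 13.1.1, re-excision for margins | does not count | does not count |

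**4. Size of the effect.** Let m be the margin-failure rate, s the rate of size-only findings, and f the share of those who have mastectomy and are counted. Then q = m + f × s. The documents give neither s nor f; both are assumptions. With m = 15%:

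| s | f = 0 | f = 0.5 | f = 1 |
|---|---|---|---|
| 2% | q = 15%: 0.904 | q = 16%: 0.864 | q = 17%: 0.814 |
| 5% | q = 15%: 0.904 | q = 17.5%: 0.785 | q = 20%: 0.609 |

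In patients, s = 2% to 5% of 79 is 1.6 to 4.0 women. With f = 1, the chance of missing an acceptable margin-failure rate rises from 0.096 to 1 − 0.814 = 0.186 or 1 − 0.609 = 0.391.

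**5. Sensitivity to m.** For f = 0 against f = 1, over s = 2% to 5%:

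- m = 10%: 0.990 falls to 0.972–0.904.
- m = 20%: 0.609 falls to 0.450–0.238.

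The effect is small if margins are rarely inadequate, and larger near the decision boundary.

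**6. Direction.** Adding size-only cases can only raise q. Against a margin-based definition, it costs power and does not raise the 5% false-go rate.

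**The case against.** The strongest reply is that the subgroup is small and may be nearly empty. Cohort 1 enters with lesions of at most 4 cm on imaging (3.1, 5.3.2), so a size-only case needs more than 1 cm of underestimation together with clear margins. Sections 10.1.1 and 13.0 name only WB-EBRT for large lesions, and 7.2.1 puts mastectomy in parentheses, so f may be well below 1. With s = 2% and f = 0.5 the loss is only from 0.904 to 0.864. The second sentence of 10.1 also lets that section be read as margin-based, in line with 13.1.1. All of this stands as a limit on size. It does not remove the conflict, because 13.1.3 and 13.2 carry no restriction to margins and 13.1.3 states a stopping rule.

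A reader might go further and infer that treatment choice affects the counts in general: that a woman with inadequate margins who declines surgery, or has WB-EBRT instead of re-excision, drops out and inflates the false-go rate. The documents do not support this. Section 13.1.1 counts need judged from the specimen, 13.1.3 counts patients who require a procedure, and 13.2 counts what was indicated, so a woman who declines still counts. For close margins, 7.2.2 puts surgery first: "Patients with surgical margins width of <2 mm following local excision and immediate IORT will be advised to undergo re-excision". It and 10.1.1 bring in WB-EBRT for margins only after re-excision. The remark in 1.2.2 b that such patients "may require the addition of WB-EBRT (with or without re-excision") is background, not a study rule. The WB-EBRT-alone category in 13.1.3 is explained by size-only cases under 7.2.1.

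**Conclusion.** The concern holds for one subgroup: DCIS above 5 cm with clear margins. For these patients the primary event is defined differently in 10.1 and 13.1.3 than in 13.1.1 and, under the former, depends on the treatment chosen. With 15% margin failures and an assumed 2% to 5% of size-only findings, P(go) runs from 0.904 with none counted to 0.81–0.61 with all counted, or 0.86–0.79 with half. These figures rest on assumed frequencies and on reading the stop at 18 as 13.1.3 words it. Under 13.1.1 alone the design keeps alpha 0.049 and power 0.904. The finding is not evidence that the counts as a whole measure treatment preference, and it gives no ground for saying that the false-go rate exceeds 5%. It is a conflict within the primary decision rule, limited to a small subgroup of unknown size, and cheap to remove.

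**What to change.** Use one event definition in 10.1, 13.1.1, 13.1.3 and 13.2, and settle it before the 25-patient interim analysis, so that it is not chosen with counts in view.

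- **Primary event:** a re-operation (re-excision or mastectomy) indicated by the margins of the initial WLE specimen, counted whatever treatment follows. The margin limit is the single value that the sponsor adopts after reconciling 7.2.2 with 10.1 and 13.0.
- **Size-only findings with clear margins:** scored the same way whichever treatment follows. Counting them under Aim 2 only fits the margin-based aim in 13.1.
- **Secondary line:** re-operations actually performed, with the reason for each.

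The cost is wording in four sections. Margin width and lesion size are already recorded (9.1, 9.3, 9.4), and the 19/25 and 62/79 cut-offs, sample size and error rates do not change. The small downside is that a mastectomy done for size alone leaves the primary rate and appears only in the secondary line. The change concerns counting only. It proposes no clinical rule and takes no view on which treatment should follow.

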8.0 ASSESSMENT OF EFFICACY AND SAFETY

- 8.1 Side effects/Toxicities to be monitored. These risks fall into four (4) general categories:
 - 8.1.1 Surgery. Complications associated with the surgical implantation of the Intrabeam PRS are similar to any tumor removal surgery. These include, but are not limited to infection, loss or impairment of nerve function, breast edema, ecchymosis, hematoma formation, wound seroma, wound dehiscence, keloid formation, skin flap necrosis, and the need for re-excision if margins are inadequate.
 - 8.1.2 Intraoperative Radiotherapy Delivery. Complications arising from the delivery of IORT include, but are not limited to infection, loss or impairment of nerve function, breast edema, fibrosis, and skin effects including dry/moist desquamation, hyperpigmentation, telangiectasia and radiation-induced skin necrosis.
 - 8.1.3 Whole-Breast External Beam Radiotherapy. Complications of WB-EBRT include, but are not limited to loss or impairment of nerve function, breast edema, fibrosis, superficial vein thrombosis, and skin effects including dry/moist desquamation, erythema, hyperpigmentation, telangiectasia and radiation-induced skin necrosis.

- 8.1.4 Diagnostic Procedures. As part of this clinical study, patients will undergo mammography, CE-MRI, and ultrasound (at the discretion of the radiologist) and will be subject to the associated risks: exposure to additional radiation, allergic reaction to MRI contrast (gadolinium), and the potential risks of additional minimally invasive breast biopsies (bleeding, hematoma, infection, and non-diagnostic or falsely negative results) that may result from the extensive imaging evaluation. The risks associated with these procedures are minimal.
- 8.1.5 Unanticipated Adverse Device Effects (UADEs) will be documented. UADEs are defined as any serious adverse effect on health or safety or any life-threatening problem or death caused by, or associated with a device if that effect, problem, or death was not previously identified in nature, severity, or degree of incidence in the investigational plan or application (including a supplementary plan or application), or any other unanticipated serious problem associated with a device that relates to the rights, safety, or welfare of subjects.
- 8.1.6 Serious Adverse Event (SAE). Serious adverse events are defined as follows: Death or threat to life; Permanent impairment of a body function or permanent damage to a body structure; or events that require medical or surgical intervention to preclude permanent impairment of a body function or permanent damage to a body structure.

Events that are considered serious include skin necrosis, non-wound healing, moist desquamation (not resolving within 4 weeks), unresolved bleeding, infection requiring medical or surgical intervention, pneumothorax, seroma/hematoma (symptomatic and/or cosmetically deforming), rib fracture, severe pain (not resolving within the first month and requiring narcotics) and wound dehiscence.

- 8.2 Dosage change based on toxicity. The prescribed dose is constant among all patients and will not be adjusted. The only variable is the time period for which the dose will be delivered. The treatment time will vary based on the lumpectomy cavity site, with total treatment time adjusted to deliver a prescribed dose of 20 Gy to the tumor surface or 5G at 1 cm depth from the tumor surface.
- 8.3 Adverse Event Reporting:
 - 8.3.1 All adverse events that occur during the study will be reported, except for observational events: cold, flu, headache, etc. The CTC guideline will be used to grade the severity of all adverse events. Adverse events not included in the CTC, version 3, will be reported with common medical terminology and grading according to definitions in the CTC:
 - 8.3.2 A description of the nature, onset, duration, severity, attribution and outcome of the occurrence will be recorded. Any treatment employed to alleviate the adverse event(s) will also be recorded.

CTC Grading of Adverse Events:

Grade 1 =	Mild adverse event
Grade 2 =	Moderate adverse event
Grade 3 =	Severe and undesirable adverse event
Grade 4 =	Life-threatening or disabling adverse event
Grade 5 =	Death related to adverse event

8.3.3 All serious adverse events will be recorded on the study data forms throughout the duration of the study.

8.3.4 The physician will document his/her opinion of the relationship of the event to the device as follows:

Unrelated = the event is clearly not related to the device
Unlikely = the event is doubtfully related to the device
Possible = the event may be related to the device
Probable = the event is likely to be related to the device
Definite = the event is clearly related to the device

8.3.5 Any serious adverse device effect, including death due to any cause, which occurs during this treatment, will be reported within 5 working days of learning of the event to Carl Zeiss, Inc. and to the IRB per the IRB requirements.

8.3.6 Serious unanticipated adverse device effects will be reported within 24 hours of learning of the event to Carl Zeiss, Inc. and to the IRB per the IRB requirements.

8.3.7 Patients who are removed from the protocol due to adverse events will be followed until the adverse event has resolved or stabilized and will continue to be followed in the intent-to-treat population. Copies of relevant documentation will be kept with the patient's protocol records.

